01	17 April 2024	[REDACTED] [REDACTED] [REDACTED] SCD Statistics	
Estimands: Provide clearer language regarding estimands. Introduce an estimand using the treatment policy strategy. Introduce another estimand using the modified treatment policy strategy. Deleting the while on treatment strategy
 
Simplification of Secondary and Exploratory Endpoints Analyses. Imputations Methodology and Tipping Point Analyses: Clarify the methodology for imputations. Provide details on tipping point analyses.
 
Analysis of SQLS and [REDACTED]: Clarification on the analysis of SQLS. Describe the analysis approach for [REDACTED].
 
Omitting Conditional Power Analysis: Exclude conditional power analysis from the study.
 
Provide clarifications in regards to: the safety analyses section the pain and tolerability section the pharmacokinetics section the biomarker and pharmacogenetic section
 
Update Appendices: Ensure that the appendices are updated accordingly.
	Response to FDA's comments on the SAP.
Original Statistical Analysis Plan	23 October 2023	[REDACTED] [REDACTED] [REDACTED] SCD Statistics	Not applicable	Not applicable

Amendment number	Date	Author(s)	Summary of changes	Reason for amendment
		[REDACTED] [REDACTED] SCD Statistics		

LIST OF ABBREVIATIONS AND DEFINITIONS OF TERMS

MedDRA	Medical Dictionary for Regulatory Activities
MI	Multiple Imputation
MM	medical monitor
MMRM	mixed-model repeated measures
MNAR	missing not at random
n	number
PANSS	Positive and Negative Syndrome Scale
PDAESI	protocol-defined adverse event of special interest
PDSS	Post-injection Delirium/Sedation Syndrome
PGI-I	Patient Global Impression-Improvement
PK	pharmacokinetics
PSP	Personal and Social Performance Scale
PT	preferred term
q1m	once monthly
R&D	Research and Development
RDQ	Readiness for Discharge Questionnaire
RTSM	Randomization and Trial Supply Management
SAS	Simpson-Angus Scale
sc	subcutaneous
SD	Standard Deviation
SE	Standard Error
SI	standard international
SOC	system organ class
SOP	Standard Operating Procedure
SQLS	Schizophrenia Quality of Life Scale
SUSAR	suspected unexpected serious adverse reaction
ULN	upper limit of normal
US	United States (of America)
WHO	World Health Organization
β-HCG	Beta-human chorionic gonadotropin

INTRODUCTION

This Statistical Analysis Plan (SAP) describes the planned analysis and reporting for Teva Branded Pharmaceutical Products R&D, study TV44749-CNS-30096, (A Multinational, Multicenter, Randomized, Double-Blind, Parallel-Group, Placebo-Controlled Study with an Open-Label, Long-Term Safety Phase to Evaluate the Efficacy, Safety, and Tolerability of Olanzapine for Extended-Release Injectable Suspension (TV-44749) for Subcutaneous Use as Treatment of Adult Patients with Schizophrenia), and was written in accordance with standard operating procedure (SOP) GSD-SOP-702 (Statistical Analysis Plan).

The reader of this SAP is encouraged to read the study protocol with amendment 01 (approved on February 15, 2024) for details on the conduct of this study, the operational aspects of clinical assessments, and the timing for completing the participation of a patient in this study.

The SAP is intended to be in agreement with the protocol, especially with regards to the primary and all secondary endpoints and their respective analyses. However, this SAP may contain more details regarding these particular points of interest, or other types of analyses (e.g., other endpoints). When differences exist in descriptions or explanations provided in the study protocol and this SAP, the SAP prevails; the differences will be explained in the Clinical Study Report.

1. STUDY OBJECTIVES, ENDPOINTS AND ESTIMANDS

This section describes the estimands and endpoints in the study. For a tabulated presentation of the efficacy endpoints with respect to the estimands see [Appendix D](#).

1.1. Primary and Secondary Study Objectives and Endpoints

The primary and secondary study objectives and endpoints are:

Objectives	Endpoints
The primary objective is to evaluate the efficacy of TV-44749 in adult patients with schizophrenia.	
The primary efficacy endpoint is as follows:
 
 • The change from baseline to week 8 in the Positive and Negative Syndrome Scale (PANSS) total score.
A key secondary objective is to further evaluate the efficacy of TV-44749 based on additional parameters in adult patients with schizophrenia.	
The secondary efficacy endpoints are as follows:
 
 • Change in Clinical Global Impression-Severity (CGI-S) scale score from baseline to week 8 • Change in Personal and Social Performance Scale (PSP) score from baseline to week 8
A secondary objective is to evaluate the safety and tolerability of TV-44749 in adult patients with schizophrenia.	
The safety and tolerability endpoints will include, where appropriate, the following: adverse events (including serious adverse events, extrapyramidal symptoms, injection pain and other injection site reactions [local tolerability]), vital signs (blood pressure, pulse and orthostatic changes, and temperature), body weight, laboratory tests, electrocardiogram (ECG), concomitant medication use, time to all-cause discontinuation, all-cause discontinuation rates and discontinuation rates due to adverse events (tolerability), and the following rating scales:
 
 • Abnormal Involuntary Movement Scale (AIMS) • Simpson-Angus Scale • Barnes Akathisia Rating Scale • Columbia Suicide Severity Rating Scale (C-SSRS) • Calgary Depression Scale for Schizophrenia (CDSS)
A secondary objective of this study is to evaluate the efficacy of TV-44749 from baseline to endpoint in Period 1 in adult patients with schizophrenia.	
 • Change from baseline to weeks 1, 2, 4 and 8 in the PANSS total score • Clinical Global Impression-Improvement (CGI-I) scale at weeks 4 and 8 • Clinical Global Impression-Severity (CGI-S) scale at weeks 1, 2, 4 and 8 • Patient Global Impression-Improvement (PGI-I) scale at weeks 2, 4 and 8 • Change from baseline to weeks 4 and 8 in the Schizophrenia Quality of Life Scale (SQLS) • Change from baseline to weeks 4 and 8 in the PSP score

1.1.1. Justification of Primary Endpoint

The primary efficacy endpoint of the study is the change from baseline to week 8 in the PANSS total score. The PANSS is a well-characterized standardized measurement used for rating

presence and severity of positive and negative symptoms in patients with schizophrenia and is widely used in the research of antipsychotic treatment.

The 30-item PANSS is used to identify the presence and severity of psychopathology symptoms, the relationship of these symptoms to one another, and global psychopathology ([Kay 1987](#)). This instrument measures the severity of positive symptoms (7 items), negative symptoms (7 items), and general psychopathology symptoms (16 items) and is the most widely used measure of symptom severity in schizophrenia drug trials. Each of the items is scored from 1 (absence of symptoms) to 7 (severe symptoms presentation). The sum of the 30 items provides the PANSS total scores, which ranges from 30 to 210 (the lower, the better the outcome). The PANSS has been shown to have high internal validity, reliability, and sensitivity to change in both short- and long-term trials ([Gopalakrishnan et al 2021](#), [Curson et al 1986](#), [Wyatt et al 1999](#)).

The PANSS will be administered by the investigator/trained rater who will evaluate a patient's current severity level of each symptom (item).

1.2. Estimands for Primary and Secondary Objectives and Endpoints

1.2.1. Primary Estimand

The purpose of the primary estimand is to evaluate the efficacy of TV-44749 compared to placebo as if patients do not withdraw and adhere to treatment as instructed (see Section 3.2.1 in the Study Protocol). Patients who withdrew from the treatment/study due to lack of efficacy or did not adhere to the investigator instructions will be regarded as if they share the slope of the placebo group from that intercurrent event (ICE) time point until week 8 (see [White et al 2019](#)). Use of prohibited antipsychotic medications is considered non-adherence to the investigator instructions unless it is short term oral use.

The clinical question of interest is as follows: "What will be the treatment benefit if a patient adheres to treatment for 8 weeks?".

For the primary efficacy objective, the following estimand attributes will be employed:

- a. **Treatment:** The treatment of low (318 mg monthly [q1m]), medium (425 mg q1m), or high (531 mg q1m) dose of TV-44749 compared to placebo, separately, will be evaluated according to the randomization assignment in Period 1.
- b. **Population:** All randomized adult patients who have a confirmed diagnosis of schizophrenia, present with acute exacerbation of disease, and are eligible for olanzapine treatment.
- c. **Endpoint:** Change from baseline to week 8 in the PANSS total score.
- d. **Population-level summary:** Difference in the means between each individual dose arm of TV-44749 and placebo for the endpoint described above.

In this study any use of antipsychotic concomitant medications is regarded as prohibited per protocol (see Section 6.7 in the protocol). However, short term oral antipsychotic medications prohibited by the protocol may be occasionally used as part of the management of acute agitation of schizophrenia exacerbation in real-life clinical practice. If such case of use of oral antipsychotic occurs, it would not be considered as effecting the primary endpoint when:

- The treatment use end date was > 14 days prior to the week 8 (Visit 11) and
- Treatment duration was ≤ 3 consecutive days and
- There were only ≤ 2 treatment episodes (where a treatment episode is defined as ≤ 3 consecutive days of treatment followed by at least 7 days without treatment) from baseline to Visit 11.

In addition, any use of prohibited antipsychotics after early termination is not considered an ICE. Prior antipsychotic medications without a defined end-date are not deemed as ICE of "prohibited concomitant antipsychotic medication" since these cases occur before randomization and initiation of treatment.

Table 1: Classification of Intercurrent Events

Intercurrent Event	Strategy	Handling of Intercurrent Events

 • Early discontinuation of treatment due to: 
 ◦ lack of efficacy ◦ disease progression • Prohibited antipsychotic (with the exception above) 	Hypothetical	Measurements after ICE will be removed and replaced with imputed data using reference-based (CIR) imputation (assuming MNAR)

 • Early discontinuation of treatment due to other reasons (including due to adverse event) 	Hypothetical	Measurements after ICE will be removed and replaced with imputed data based on randomized treatment group (assuming MAR)

 • Allowed concomitant medications • Adverse event that did not lead to treatment discontinuation • Use of prohibited medications that are not antipsychotic • Short term use of prohibited antipsychotic (see meeting the definition above) • Injection site reaction • Out of window safety assessments 	Treatment policy	Measurements after ICE will be included in the primary analysis

ICE=intercurrent event; MAR=missing at random; MNAR=missing not at random; CIR = copy increments in reference

Any data collected after the intercurrent event (ICE) of taking prohibited antipsychotic medications (except as described above) or withdrawal from randomized treatment due to insufficient clinical response (i.e., lack of efficacy) will be treated in the analysis as MNAR. An ICE of early discontinuation for other reasons will be treated in the analysis as if the patient fully complied and completed the study (i.e., assuming missing at random [MAR]); see Table 1 for further details on the classification and handling of ICEs. This complies with the hypothetical approach.

For ICEs that were not foreseen at the time of writing the protocol and that require the use of the hypothetical strategy, classification as MAR/MNAR and revisiting this classification will be done in a blinded manner on a case-by-case basis prior to database lock for efficacy and will be

documented in the blinded statistical data review meeting minutes (see Section 5.7). Likewise, the classification of ICEs as stated in Table 1 will be conducted in a blinded manner before database lock for efficacy and documented accordingly. The reference-based CIR approach (White et al 2019) is described in Section 6.2.3 of this document.

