1.2.2. Key Secondary Efficacy Estimand

For the key secondary efficacy objectives, attributes “a” and “b” will be implemented in the same manner as planned for the primary estimand:

- a. Treatment:** The treatment of low, medium, or high dose of TV-44749 compared to placebo, separately, will be evaluated according to the randomization assignment at Period 1.
- b. Population:** All randomized adult patients who have a confirmed diagnosis of schizophrenia, present with acute exacerbation of disease, and are eligible for olanzapine treatment.
- c. Endpoint:** Change in Clinical Global Impression-Severity (CGI-S) scale score from baseline to week 8 and change in Personal and Social Performance Scale (PSP) score from baseline to week 8.
- d. Population-level summary:** Details are described in Section 6.4.

Any data collected after the ICE of taking prohibited antipsychotic medications (that is not short term) or withdrawal from randomized treatment due to insufficient clinical response (lack of efficacy) will be regarded as patients not reaching the optimal treatment effect (ie, MNAR). The ICE of early discontinuation for other reasons will be regarded as if the patient fully complied and completed the study (assuming MAR); see Table 1 for further details on the classification and handling of ICEs. This complies with the hypothetical approach.

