Patients must have an identified responsible person (referred to as the caregiver) who has agreed to provide information about the patient's location, condition, and overall status during outpatient portions of the study during Period 1. The patient's caregiver will be asked to sign a caregiver ICF during the screening period.

Patients who are not already in an inpatient setting will be hospitalized during the screening period (see details pertaining to hospitalization duration and discharge criteria in the description of "Period 1" below).

Patients will taper off their prior oral antipsychotic medications at rates per the investigator's discretion. The tapering-off process should be completed prior to randomization.

Patients entering the study who have not previously received oral olanzapine will receive 2 oral doses of olanzapine for 2 consecutive days during the screening period (the second dose should be administered at least 24 hours prior to randomization) to assess patient tolerability (oral olanzapine 10 mg/day or higher [but not exceeding 20 mg/day] per investigator decision). The PANSS and Clinical Global Impression-Severity (CGI-S) should be completed prior to oral olanzapine administration.

Patients who received olanzapine within the last year will not be required to receive the 2 doses of oral treatment. The investigator will verify the previous use, tolerability, and duration of olanzapine treatment to assure prior tolerability.

In the event that a patient meets all study inclusion criteria and does not meet any of the study exclusion criteria, but results of screening blood and urine samples taken within the 8-day screening period are not available by day 8 of screening, the screening period may be extended by 2 days (until day 10 of screening) to allow the receipt of the results to confirm patients'

eligibility. In case results are not available by day 10, the patient will be considered a screening failure and may be considered for rescreening. In addition, the screening period may be extended by 2 days (until day 10 of screening), in exceptional cases, due to special conditions (e.g. extreme weather) after receiving approval from the MM or sponsor.

Period 1 (8 weeks):

Period 1 is an 8-week double-blind, placebo-controlled, efficacy and safety period (acute treatment phase).

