4.3.5. Handling of Concomitant Medication with Missing Dates

For determination of prior vs. concomitant medication, missing start or end month are imputed to January or December, respectively, and missing start or end days are imputed to day 01 and 30, respectively, unless the month is not missing then a missing day is imputed to 28. Missing dates for oral Olanzapine administered in the screening period (as part of the predefined study procedures, in accordance to the description in the study protocol) will not be imputed.

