6.2.3. Multiple Imputation Methods

For ICEs using the hypothetical strategy (Section 1.2.1), data collected after the ICE will be handled as analysis missing, and a multiple imputation method will be used to handle this missing data.

For ICEs of early discontinuation of randomized treatment due to lack of efficacy/disease progression, or use of prohibited antipsychotic medication that are not part of the management of patients with schizophrenia (see Section 1.2.1), imputations will be performed assuming Copy Increment from Reference (CIR) in order to estimate what would have happened if patients who discontinued early had remained in the study and had a similar ('trend') slope to patients on placebo group from the time of ICE onward (White et al 2019).

For ICEs of early discontinuation of randomized treatment due to a reason that is not lack of efficacy, imputations will be performed using MAR, i.e., assuming that the clinical effect in these patients is similar to those in the same treatment arm that did not experience an ICE during the study.

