8.10. Concomitant Medications or Therapies

Concomitant therapies and medications, including medications that are taken on an as needed basis and occasional therapies, will be monitored and recorded during the study. Details of prohibited medications may be found in Section 6.7 of the study protocol. All concomitant medications will be coded using the WHO Drug.

The incidence of concomitant therapies and medications will be summarized by therapeutic class category and preferred term using descriptive statistics. Patients are counted only once in each therapeutic class, and only once in each preferred term category. Concomitant therapies and medications will include all medications up to the end of study as defined in the study protocol. This will also include medication that a patient had started taking before entering the study as long as the patient had continued to take this medication during the study.

A separate summary will be presented for Period 1 and for the integrated study periods. A separate safety summaries will be presented for the On Treatment period (baseline visit until EOT visit, including ET if conducted during this period) and for the Follow-Up period (any visit after the End of Treatment/Early Termination visit until the end of the study).

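### Three SAP rules on antipsychotic use and early discontinuation do not match the main intercurrent-event definition or the protocol, so a few PANSS values could be kept, or imputed, under the wrong assumption

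*SAP*

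**What the plan says.** **Master rule.** SAP 1.2.1 states: "Use of prohibited antipsychotic medications is considered non-adherence to the investigator instructions unless it is short term oral use". Exempt oral use must have ended more than 14 days before the week 8 visit, lasted at most 3 consecutive days, and occurred in at most 2 episodes. Table 1 sends other prohibited antipsychotic use to copy-increments-in-reference (CIR) imputation, which assumes data missing not at random (MNAR). Before lock, "the classification of ICEs as stated in Table 1 will be conducted in a blinded manner".

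**Restatements.** SAP 1.2.2 describes the intercurrent event (ICE) as "taking prohibited antipsychotic medications (that is not short term". SAP 6.2.3 applies CIR to "use of prohibited antipsychotic medication that are not part of the management of patients with schizophrenia". In Appendix B, the code 2 row begins from documented oral use. Code 1 covers termination for lack of efficacy or an adverse event of exacerbation, and code 3 all other terminations.

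**Undated prior drugs.** SAP 1.2.1 adds that "Prior antipsychotic medications without a defined end-date are not deemed as ICE", because they are taken to precede randomization. SAP 2.1 says of the screening taper: "The tapering-off process should be completed prior to randomization". To separate prior from concomitant drugs, SAP 4.3.5 fills in incomplete dates: "missing start or end month are imputed to January or December, respectively". SAP 8.10 counts as concomitant any "medication that a patient had started taking before entering the study as long as the patient had continued to take this medication" during the study.

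**Protocol.** Table 4 in protocol 3.2.1 puts suicide, and early discontinuation due to lack of efficacy, prohibited antipsychotic or disease progression, under MNAR. Protocol 10.5.6.1 keeps death out of the group imputed as missing at random (MAR). SAP Table 1 omits suicide and lists prohibited antipsychotic only as use, not as a reason for discontinuing. SAP 6.2.3 gives MAR to every reason other than lack of efficacy, with no exception for death.

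**The concern.** These rules decide whether a patient's later PANSS scores are kept, replaced by CIR, or replaced under MAR. If the row that assigns the code is narrower than the definition it implements, a programmer following it keeps scores that the estimand removes. If a missing end date is taken as proof that a drug was stopped, scores obtained on another antipsychotic can count as the effect of the randomized arm. If protocol MNAR events move to MAR without being declared, the primary analysis differs from the protocol in a way that Section 17 does not show. A choice settled by clear text before unblinding is routine; the same choice made afterwards would look discretionary.

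**Working it through.** **1. The plan's own window.** Week 8 is nominally Day 57. Ending more than 14 days earlier means ending by Day 57 − 15 = 42, which is 6 weeks. This agrees with the six weeks given in SAP 17.1, so that part of the rule is consistent.

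**2. Which antipsychotic use escapes CIR, reading each place on its own words.**

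| SAP place | Use that escapes CIR | Link back |
|---|---|---|
| 1.2.1 | Oral, within the 14-day, 3-day and 2-episode limits | Master text |
| Table 1 | Use meeting the exception above it | To 1.2.1 text |
| 1.2.2 | Any short-term use; no route or limits | To Table 1 |
| 6.2.3 | Use that is part of managing schizophrenia; no route or limits | To 1.2.1 |
| Appendix B, code 2 | All non-oral use, plus oral use meeting the 1.2.1 conditions | To 1.2.1 |

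Take one record: a single rapid-acting intramuscular antipsychotic injection for agitation (protocol 2.1.2 describes such a formulation). Under 1.2.1 it is not oral, so later scores are removed and imputed by CIR. Under the code 2 row it gets no code, so later scores stay as observed. If the patient later stops for another reason, code 3 applies MAR from that point.

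**3. Undated prior drugs.** SAP 5.5 defines prior medication as anything taken before first dose, so a drug can be both prior and concomitant. A drug still being taken has no end date, so the exemption literally covers it. The text does not say whether a partial date counts as a defined one. Suppose only the end day is missing and the stop month is the month of first dose. SAP 4.3.5 sets the day to 28, which falls on or after first dose for 12 × 28 = 336 of the 365 dates in 2023, or 92%. SAP 4.3.5 and 8.10 then make the drug concomitant, while the 1.2.1 exemption may treat it as ended. SAP 4.3.5 has no rule for a missing year.

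**4. Protocol against SAP.**

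- Suicide: MNAR in protocol Table 4; absent from SAP Table 1 and Appendix B.
- Death: excluded from MAR in protocol 10.5.6.1; exclusion absent from SAP 6.2.3.
- Discontinuation due to prohibited antipsychotic: MNAR in protocol Table 4; absent from SAP Table 1 and Appendix B, while SAP 1.2.1 also says that use after termination is not an ICE.
- Disease progression: kept in SAP Table 1 and 6.2.3; absent from Appendix B code 1.
- Section 17: 17.1 declares only the short oral use change to the primary estimand.

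**5. Size.** The documents give no counts (17.1 speaks only of few cases) and the SD is redacted, so these inputs are assumptions. With 675 randomized by 29 January 2024 (protocol amendment details), n per arm = 675/4 = 168.75. For an assumed SD of 18 to 22, SE = SD × √(2/168.75) = 1.96 to 2.40, ignoring missing data and covariates.

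- *Rules 1 and 2.* Assume that a kept score differs from its CIR value by 8 to 12 points. Per net case: 8/168.75 = 0.047 to 12/168.75 = 0.071 points. Five net cases: 0.24 to 0.36 points, or 0.237/2.40 = 0.10 to 0.356/1.96 = 0.18 SE. A 0.5-point shift needs 0.5 × 168.75/12 = 7.0 to 0.5 × 168.75/8 = 10.5 net cases.
- *Rule 3.* CIR and MAR coincide in the placebo arm. In an active arm they differ by the divergence from placebo still to come after the stop, assumed to be 0 to 6 points. Per case: 0 to 6/168.75 = 0.036 points. Five cases: 0 to 0.18 points, at most 0.178/1.96 = 0.09 SE, and zero if the arms have already plateaued.

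**The case against.** The best answer is that the SAP already has one definition. Table 1, 6.2.3 and Appendix B point back to 1.2.1, and 1.2.2 points to Table 1. Potential ICEs are reviewed blinded before lock (SAP 5.7), patients are inpatients for at least four weeks, and the taper should be finished before randomization. The planned analyses include MAR for all ICEs, a two-way tipping point, treatment policy and modified treatment policy. The SAP prevails over the protocol, and protocol 3.2.1 lets the classification be revisited blinded.

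Much of this stands. The cross-references largely answer the loose wording in 1.2.2 and 6.2.3. They do not cure code 2, whose own subject is oral use. Blinding prevents a biased choice but does not say which text applies. The MAR and tipping-point analyses act on scores already set to missing, so they would not reach an uncoded case. Precedence of the SAP settles which text governs, but SAP 2.6.2 still promises that changes and reasons will be described in the SAP.

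Three stronger readings are tempting and not supported:

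- A reader might use the imputed dates of 4.3.5 to show that an undated drug exceeds the 3-day limit. Nothing in the SAP applies those dates to the length of an ICE.
- A reader might route deteriorating patients to MAR through the CRF reason about needing a prohibited drug. Protocol 5.4 gives that reason for an adverse event not itself severe enough to stop treatment.
- A reader might carry the post-termination exemption of 1.2.1 into the modified treatment policy estimand in 1.2.4. No text does so.

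**Conclusion.** The point holds as a specification defect in three places. Code 2 is narrower than the definition it implements. The undated-drug exemption rests on an unproven premise: applying it follows the letter of 1.2.1, but it conflicts with 4.3.5 and 8.10 and with the aim of the estimand. The loss of protocol MNAR categories is real and undeclared, although the protocol is not uniform either: the closing text of 3.2.1 and 10.5.6.1 do not repeat discontinuation due to prohibited antipsychotic.

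The likely effect is small. For the first two rules it can go either way, favouring TV-44749 if such use is commoner on active treatment and working against it if commoner on placebo. For the third it is nil, or favours TV-44749 while the arms are still diverging. All sizes rest on assumed case counts, per-patient differences and SD. A reader might infer that the primary result is at risk, but the documents do not support that. Even 5% against 0% affected at 12 points each gives 0.60 points, about 0.3 SE, and nothing in the documents suggests so large an imbalance.

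**What to change.** 1. **Code 2 and wording.** Delete the word oral from the Appendix B code 2 row. In 1.2.2 and 6.2.3, replace the loose phrases with a reference to use not meeting the short-term oral criteria of 1.2.1.
2. **Undated prior drugs.** In 1.2.1, limit the exemption to records where the blinded review finds that the drug was stopped before randomization. State whether a partial date counts as defined and whether 4.3.5 applies to ICE classification. Query the remaining records, and classify documented continued use as a prohibited-antipsychotic ICE.
3. **Protocol categories.** Restore suicide and discontinuation due to prohibited antipsychotic in Table 1 and Appendix B code 1, add disease progression to code 1, and state in 6.2.3 how death is handled. If the change is intended, declare and justify it in Section 17 instead.

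The cost is SAP wording and a few blinded queries and re-codings at the statistical data review meeting already planned. No new data collection or change to trial conduct is needed. The changes must be made before the efficacy lock.
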